10.3 Escape Therapy

Subject who cannot adhere to the protocol-defined steroid taper due to flare/relapse must discontinue study drug (KPL-301 or placebo) and should receive escape therapy in accordance with local SoC per the Investigator. Escape therapy may include, for example, prednisone or similar > 60mg/day, IV corticosteroids, other immunomodulatory agents, and/or approved therapies (e.g., tocilizumab). These subjects are considered to have met the primary endpoint provided the flare occurs prior to Week 26.

Escape corticosteroid therapy can be escalated immediately. Due to unknown possible safety and pharmacological effects from overlapping exposures to immunomodulatory agents on top of co-administered corticosteroids, the investigator should consider a washout period of at least 35 days (based on elimination half-lives) after the last dose of study drug (KPL-301 or placebo) if deemed clinically appropriate.

10.4 Treatment Compliance

Subject compliance will be assessed by maintaining adequate administration records. Adherence to study drug administration (KPL-301/placebo and prednisone for the steroid taper) will be assessed during the study site visits. Subjects will be given a diary to record home injections of KPL-301 or placebo and intake of prednisone tablets. Subjects will be asked to return all used supply containers as well as any unused study medication at each visit along with their diary as a measure of drug accountability and subject compliance. Investigator staff may contact patients between visits to ensure compliance with protocol specified treatment regimens.

Sharps containers for any used prefilled syringes will be provided to the subjects for home usage. After home injections the used syringes must be placed into the sharps containers immediately. The sharps containers should be returned to the sites and discarded by the site staff as per local site procedure.

11 Study Periods

11.1 Screening Period

After provision of written informed consent for the study, patients will be screened for study eligibility within 6 weeks before Day 0 (first dose).

Results of SoC tests or examinations performed prior to obtaining informed consent within 6 weeks prior to Day 0 may be used; such tests do not need to be repeated for screening. Other tests required by the protocol will be conducted and reimbursed by the Sponsor as necessary. Written informed consent for study participation must be obtained before performing any study-specific screening tests or evaluations. All screening activities must be completed and eligibility confirmed before randomizing subjects and administering study drug.

The Investigator will maintain a screening log to record details of all patients screened and to confirm eligibility or record reasons for screening failure, as applicable. Prior to first administration of KPL-301, all subjects are required to have achieved remission (i.e., resolution of GCA symptom(s) and CRP < 1.0 mg/dL or ESR < 20 mm in the first hour). Should a subject in screening not achieve remission by

> 6 weeks of onset they can be rescreened following the relapsing/refractory non-remitting inclusion criteria.

Refer to the Schedule of Activities in [Table 1](#) for activities required during screening.

11.2 Double-blind Period

Following signing of the ICF and successful completion of the screening procedures, eligible subjects will be randomized 3:2 to blinded treatment with KPL-301 or placebo administered SC every other week (every 2 weeks) in the double-blind treatment period coadministered with a 26-week oral corticosteroid taper.

The first administration of subcutaneous KPL-301/placebo and oral prednisone taper will take place at the study site on Day 0. Subsequent doses of KPL-301/placebo will be administered at the study site in conjunction with a scheduled study visit or dispensed to the subject for outpatient administration. All subjects will receive oral prednisone, which will be tapered down during the double-blind base period according to a standardized tapering protocol. The steroid taper will be self-administered by study subjects on a daily basis. Subjects will be followed at the study site at Weeks 1, 2, 3, 4, and approximately every 4 weeks thereafter until week 26 (see [Table 1](#)). Subjects reporting worsening of GCA symptoms or any safety issues may be brought in for an unscheduled visit at the study site at any time.

Subjects who experience a flare or who cannot adhere to the protocol-defined steroid taper due to flare/relapse must discontinue the assigned study drug (KPL-301 or placebo) and should receive escape therapy in accordance with local SoC. These subjects will be considered to have met the primary endpoint if a flare has occurred prior to Week 26.

Any subject who prematurely discontinues the study drug treatment for safety or other reason will have an EOT visit and will be followed for safety for the intended duration of the study to address potential issues of informative censoring. Any subject who withdraws consent from the trial (i.e., all study procedures in addition to study drug) must complete an EOT visit then proceed to the Washout Safety Follow-up Period or at a minimum have a Final Washout Safety Follow-up visit 84 ± 3 days from the last dose administered. Additional follow up using public records may be captured where possible.

12 Study Procedures

12.1 Screening and Randomization Procedures

12.1.1 Informed Consent

Written informed consent for participation in the study must be obtained before performing any study-specific screening test or evaluations. ICFs for all patients who are enrolled or who failed screening will be maintained at the study site.

12.1.2 Medical History and Demographics

General medical history and subject demographic information will be recorded on eCRF. Additional information will be captured related to GCA including disease duration, history of prior flare/relapse, as well as history of allergy or anaphylaxis. In addition, subjects will be asked to report their current use and history of tobacco and smoking as well as provide more detailed information on pulmonary history.

12.1.3 Eligibility

All subjects screened will be assessed for eligibility for randomization into the study according to the inclusion/exclusion criteria ([Section 8.7](#)). A master log will be maintained of all enrolled subjects and will

document all screening failures (i.e., subjects who are enrolled but not randomized), including reason for screen failure.

12.1.4 Subject Randomization

An Interactive Web Response System (IWRS) will be used for assignment of the Subject Identification Number at enrollment, randomization to a treatment arm (KPL-301 or placebo), and assignment of blinded investigational product. A subject is considered randomized into the study when the Investigator confirms the eligibility criteria in the IWRS and the pharmacist has been provided with the investigational product number.

12.2 Clinical GCA Related Assessments

12.2.1 Clinical GCA Assessments

Ideally clinical assessments of GCA signs/symptoms should occur prior to the investigator reviewing subject imaging, lab or acute phase reactant results at any given visit to minimize potential for assessment bias.

- Cranial symptoms
 - New or recurrent headache or pain or tenderness of the scalp or the temporal artery
 - Visual signs/symptoms such as ischemic retinopathy, optic neuropathy, diplopia, amaurosis fugax, etc.
 - New or recurrent claudication of the tongue, masseter muscle, or worsening temporal artery signs and symptoms
 - TIA or stroke related to GCA in the opinion of the Investigator
- Extracranial symptoms
 - Classic PMR-like symptoms, defined as shoulder and/or hip girdle pain associated with inflammatory morning stiffness
 - New or recurrent claudication in the peripheral circulation (i.e., in one of the extremities)
- New or worsening angiographic abnormalities detected via MRI, CT/CTA, or PET-CT of the aorta or other great vessels or via ultrasound of the temporal arteries

Supportive findings could include other symptoms in the opinion of the Investigator related to worsening GCA, such as sustained daily recurrent fever with a temperature over 38°C for more than 1-week, chronic anaemia, or unexplained weight loss.

All elements of the diagnostic work-up pertinent to the Investigator diagnosis of GCA should be reviewed with the CRO-designated Medical Expert and entered into the eCRF promptly.

12.2.2 TAB

New-onset subjects can have an optional temporal artery biopsy taken at Screening and Week 26 as part of the study. For relapsing/refractory patients, if the subject has not had a prior a temporal biopsy an optional biopsy can be done at Screening and Week 26. If the subject has an existing biopsy sample available this can be submitted as the screening/predose sample and an optional biopsy can be performed at Week 26. Temporal biopsy specimens if available will be submitted to the central laboratory.

12.2.3 Imaging (MRI, CT, PET, or Ultrasound)

Evidence of large-vessel vasculitis by angiography or cross-sectional imaging study such as MRI, CT/CTA, or PET-CT of the aorta or other great vessels should be performed according the schedule of activities (Table 1).

In cases where ultrasound of temporal artery was captured during the diagnosis of GCA at Screening, this procedure should be repeated at Weeks 12, 26, EOT and Week 38 as well as any instances of suspected flare over the course of the study. Imaging and relevant data should be included in any elements of the diagnostic work-up pertinent to the Investigator diagnosis of GCA.

12.2.4 CRP and ESR

Central laboratory assessments of CRP and local assessment of ESR will be performed at each study visit. Centrally determined laboratory values will be used for statistical evaluations and report writing. CRP changes and the time course to decrease and resolve CRP to normal values ≤ 0.5 mg/dL will be assessed.

If necessary local CRP tests can be used by the site to support the Investigator's clinical decisions regarding the GCA status.

12.3 Physical Examination and Vitals

12.3.1 Physical Exam

A complete physical examination as possible by local practice should include an evaluation of the head, eye, ear, nose, and throat as well as cardiovascular, dermatological, musculoskeletal, respiratory, gastrointestinal, genitourinary, and neurological systems. Any abnormality identified at baseline should be recorded on the Medical History and Physical Examination eCRFs.

At subsequent visits, limited symptom-directed physical examinations may need to be performed in order to determine changes from baseline abnormalities and should be recorded in the subject's trial notes. New or worsened abnormalities should be recorded as AEs on the Adverse Event CRF.

12.3.2 Vital Signs

Vital signs will include measurements of respiratory rate, pulse rate, systolic and diastolic blood pressure, and temperature. Blood pressure measurements should be obtained after the subject has been seated for at least 5 minutes.

12.3.3 Body Weight and Height

Body weight and height will be measured as per SoC at the study site and will be recorded in the eCRF.

12.4 Electrocardiogram

Twelve-lead ECGs will be performed at Screening at the study site and may be performed at an unscheduled visit if determined necessary by the Investigator during the treatment period. To minimize variability, ECGs should be performed prior to meals and any scheduled vital sign measurements and blood draws. Subjects should be in a resting position for ≥ 10 minutes prior to ECG and body position should be consistently maintained and environmental distractions (e.g., TV, radio) should be avoided to prevent changes in heart rate during recording.

The digital ECG recording must be obtained and reviewed by the Investigator or designee. For safety monitoring purposes, the Investigator or designee must sign and date all ECG tracings and place the paper

copy as part of the subject's permanent study file at the site and overall ECG interpretation will be documented in eCRF.

12.5 Respiratory Evaluations

12.5.1 PFTs and DLCO

PFTs and DLCO should be obtained at Screening within 6 weeks prior to Day 0, or existing documentation within 12 weeks of day 0 can be used and reviewed by the Investigator or designee. During the course of the study PFTs and DLCO should be obtained at Weeks 12, 26 and 38 with a window of ± 14 days.

12.5.2 Chest X-Ray

Chest X-rays in accordance with local requirements should be obtained at Screening (or existing chest X-ray within 12 weeks of Day 0 can be used) and reviewed by the Investigator or designee. X-rays should be reviewed to show no clinically significant abnormality and no signs or symptoms suggestive of pulmonary disease that would exclude the potential subject.

12.5.3 TB Screening

Eligibility will be determined based on a central QuantiFERON TB test performed during screening in order to evaluate (active, untreated, or partially treated latent) infection with TB.

If a patient is suspected to have contracted tuberculosis during the study the study site may conduct a TB test in accordance with the site's normal practice to diagnose TB (PPD or local QuantiFERON).

12.5.4 Dyspnea Score and O₂ Saturation

The modified Borg scale ([Borg and Borg, 2010](#)) is a validated patient reported outcome and will be used to assess subjects' perceived sensation of difficulty in breathing (dyspnea) while resting. This scale is a linear scale of numbers ranking the magnitude of difficulty in breathing, ranging from 0 (nothing at all) to 10 (maximal). A validated version of the Borg scale in local language will be provided.

Oxygen saturation will be assessed as part of respiratory system assessment. Pulse oximetry must be performed before PFTs and should be done with the subject in a seated position after a 10-minute period of rest. It is important that the pulse oximetry be performed in the same center throughout the study since oximetry readings vary with changes in altitude.

12.6 Laboratory Assessments

Laboratory assessments should be collected as per the schedule of activities ([Table 1](#)). Unscheduled laboratory assessments for safety issues are permitted as deemed necessary by the Investigator. The procedures for the collection, handling, and shipment of laboratory samples are specified in the Laboratory Manual supplied to sites by the central laboratory.

Local laboratory tests and values may be used by the Investigator as necessary to support clinical decisions but will not be captured as part of the study for analysis.

12.6.1 Serology

Rheumatoid factor, protein electrophoresis, HbsAg, HbsAb, HbcAb and HCVAb: collected at Screening only unless clinically indicated during the study.

12.6.2 Hematology

White blood cell count with differential, platelet count, red blood cell count, mean corpuscular volume, hemoglobin, mean corpuscular hemoglobin concentration.

12.6.3 Chemistry

Urea, uric acid, creatinine, glucose, potassium, sodium, chloride, calcium, phosphorus, total protein, albumin, creatinine phosphokinase, C3, and C4.

12.6.4 Liver Profile

AST, ALT, alkaline phosphatase (ALP), and total bilirubin (direct and indirect will be performed if total bilirubin is greater than the ULN).

Tests for AST, ALT, ALP and total bilirubin must be conducted and assessed concurrently. Additional test may be used for follow up if values come back abnormal.

12.6.5 Fasting Lipid Panel and HbA1c

[figure not shown]
Whenever possible laboratory samples should be drawn in the morning. Subjects should fast overnight (> 8 hours) prior to blood sampling at clinic visits. Subjects will be allowed to drink only water during this time. The following panels will be taken: HbA1c, total cholesterol, triglycerides, high-density lipoprotein, low-density lipoprotein, apolipoprotein A, and apolipoprotein B.

[figure not shown]
[figure not shown]
12.6.6 Urinalysis

Specific gravity, pH, protein, urobilinogen, ketones, glucose, blood, bilirubin, nitrite, leukocyte esterase, creatinine.

12.6.7 Pregnancy Test

For women of child bearing potential a serum pregnancy test should be performed prior to randomization at the site. Urine pregnancy tests should be performed at Day 0, Week 12, Week 26 and the Final Washout Safety Follow-up Visit. Abnormal laboratory results should be repeated as soon as possible (preferably within 24 to 48 hours).

13 Safety Assessments

13.1 Adverse Events

13.1.1 Adverse Event Definition

An AE is any untoward medical occurrence in a subject or clinical investigation subject administered a pharmaceutical product. An AE does not necessarily have a causal relationship with this treatment. An AE can therefore be any unfavorable and/or unintended sign (including an abnormal laboratory finding), symptom or disease temporally associated with the use of a medicinal (investigational) product, whether or not related to the medicinal (investigational) product.

AEs also include: any worsening (i.e., any clinically significant change in frequency and/or intensity) of a pre-existing condition that is temporally associated with the use of the study drug; abnormal laboratory findings considered by the reporting Investigator to be clinically significant; and any untoward medical occurrence.

13.1.2 Management of Specific Disease Related Events

Signs, symptoms and abnormal findings associated with active GCA should not be captured as Adverse Events in this study but rather as flare related efficacy endpoint findings. If there are questions regarding how to classify these events, Investigators should consult with the CRO-designated Medical Expert.

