If a flare/relapse is suspected during the treatment period, the Investigator must consult the Contract Research Organization (CRO)-designated Medical Expert to review and harmonize the elements of the diagnostic work-up. Flare/relapse is defined as a re-increase of CRP from normal to 1 mg/dL or greater and/or of ESR from less than 20 mm in the first hour to 30 mm or greater AND at least one of the following signs or symptoms attributed by the Investigator to new, worsening, or recurrent GCA:

- Cranial symptoms
 - New or recurrent headache or pain or tenderness of the scalp or the temporal artery
 - Visual signs/symptoms such as ischemic retinopathy, optic neuropathy, diplopia, amaurosis fugax, etc.
 - New or recurrent claudication of the tongue, masseter muscle, or worsening temporal artery signs and symptoms
 - Transient ischemic attack (TIA) or stroke related to GCA in the opinion of the Investigator
- Extracranial symptoms
 - Classic PMR-like symptoms, defined as shoulder and/or hip girdle pain associated with inflammatory morning stiffness
 - New or recurrent claudication in the peripheral circulation (i.e., in one of the extremities)
- New or worsening angiographic abnormalities detected via MRI, CT/CTA, or PET-CT of the aorta or other great vessels or via ultrasound of the temporal arteries

Supportive findings could include other symptoms in the opinion of the Investigator related to worsening GCA, such as sustained daily recurrent fever with a temperature over 38°C for more than 1 week, chronic anemia, or unexplained weight loss.

Although either acute phase reactant (CRP or ESR) may be used during the study for eligibility and to determine remission or flares, it is advisable that the same acute phase reactant used to determine remission at screening also be used to determine flares during the treatment period.

All elements of the diagnostic work-up pertinent to the Investigator diagnosis of a flare/relapse (i.e., the primary efficacy endpoint) should be reviewed with the CRO-designated Medical Expert and entered into the electronic Case Report Form (eCRF) promptly.

Flare/relapse is defined as major if cranial symptoms or ischemia-related visual loss are present or if there is clear evidence of new onset large vessel vasculitis (e.g., subclavian artery). In all other situations, flare/relapse attributed to PMR, vascular or other symptoms should be regarded as minor.

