13.1.6 Serious Adverse Event

A serious adverse event (SAE) is any untoward medical occurrence or effect that, at any dose:

- Results in *death* – Includes all deaths, even those that appear to be completely unrelated to study drug (e.g., car accident where subject is a passenger)
- Is *life-threatening* – in the view of the Investigator, the subject was at immediate risk of death from the event at the time of the event (i.e., it does not include an AE that might have caused death if it had occurred in a more serious form).
- Requires *in-patient hospitalization* or prolongs an existing hospitalization. (Complications occurring during hospitalization are AEs and are SAEs if they cause prolongation of the current hospitalization. Hospitalization for elective treatment of a pre-existing non-worsening condition is not, however, considered an AE. The details of such hospitalizations must be recorded on the medical history or physical examination page of the eCRF. Hospitalization is defined as an admission to the hospital ward or a short-stay-type unit longer than 24 hours. Prolongation of existing hospitalization is defined as hospital stay longer than originally anticipated for the event or development of a new AE as determined by the Investigator or treating physician.
- Results in *persistent or significant disability/incapacity* (an AE is incapacitating or disabling if it results in a substantial and/or permanent disruption of the subject’s ability to carry out normal life functions).
- Is a congenital anomaly/birth defect.
- Is an *important medical event* – Important medical events may not be immediately life-threatening or result in death or hospitalization but may jeopardize the subject or may require intervention to

prevent one of the other serious outcomes listed above (e.g., intensive treatment in an emergency room or at home for allergic bronchospasm; blood dyscrasias or convulsions that do not result in hospitalization; or development of drug dependency or drug abuse).

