In addition, medical and scientific judgment is required to decide if prompt notification is required in situations other than those defined for SAEs above, i.e., any event that the Investigator regards as serious that did not strictly meet the criteria above but may have jeopardized the subject or required intervention to prevent one of the outcomes listed above, or that would suggest any significant hazard, contraindication, side effect, or precaution that may be associated with the use of the IMP.

All SAEs that occur after signing of study-related informed consent, whether or not the SAEs are related to the study drug or study procedures, must be reported.

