13.6 Reporting Serious Adverse Events

All SAEs, whether or not considered causally related to study drug or to the study procedure(s), have to be reported. SAEs will be recorded in the eCRF within 24 hours of discovery.

In case the eCRF is inaccessible, the Investigator must report all SAEs to the Safety Department and Sponsor within 24 hours of discovery via the SAE reporting form to:

24 Hour Safety [contact]

24 Hour Safety Hotline [contact]

US 24 Hour Safety [contact]

US 24 Hour Safety Hotline [contact]

Additional follow-up information, if required or available, should be sent to the Safety Department within 1 business day of receipt and placed with the original SAE information and kept with the appropriate section of the eCRF and/or study file.

Information on non-serious AEs that become serious must also be reported to the Safety Department as soon as it is available.

Investigators must report SAEs and follow-up information to their responsible Institutional Review Board (IRB) or Independent Ethics Committee (IEC) as applicable per institutional policy.

The Sponsor or designee will provide regulatory authorities, IRBs, IECs, and principal investigators with clinical safety updates/reports according to local requirements.

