**Table 1: Censoring Rules for Time to Flare by Week 26**

	Scenario	Event or Censoring	Censoring Reason	Date of Event or Censoring
1	Flare occurrence on or prior to week 26	Event	No censoring	Date of flare
2	No flare occurrence on or prior to week 26	Censored	No flare occurrence	Date of last assessment by week 26
3	No flare occurrence on or prior to EOT	Censored	No flare occurrence by EOT	Date of last assessment by EOT
4	No post baseline assessment	Censored	No assessment	Date of randomization

Time to flare by week 26 will be summarized by the 25th, 50th (median), and 75th percentiles calculated using the Kaplan-Meier (KM) method to estimate the survival functions for each treatment group. The 95% confidence interval (CI) for the percentiles will be calculated using a log-log transformation. Plots of survival curves by treatment using the KM method will be presented. Additional survival plots will be provided by treatment for the stratification factor.

A log-rank test stratified by the stratification factor (disease status) will be used as the primary treatment comparison between KPL-301 and placebo. To describe the magnitude of treatment effect, the hazard ratio for KPL-301 compared to placebo and the corresponding Wald 95% CI will be

calculated based on a Cox proportional-hazards model with treatment as a covariate and stratified by the stratification factor.

If subjects were randomized based on incorrect stratum, then the corrected stratum will be used for stratified analyses rather than the incorrect stratum recorded at randomization.

The primary analysis of time to flare will be based on the adjudication outcome. Time to flare per investigator's assessment will be used as a supportive analysis of the primary endpoint. A 2x2 table of concordance will be used to assess the agreement between adjudicated and investigator assessments.

As a sensitivity analysis, the stratified analyses of time to flare based on adjudication will be repeated for the per protocol analysis set defined in Section 2.3 .

The stratified analyses of time to flare based on adjudication will also be repeated for the mITT analysis set by censoring subjects without flare before EOT at the last assessment date by week 26. That is, the censoring does not take into consideration of the early treatment discontinuation. The scenario 3 in the censoring table follows scenario 2 rule.

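### Protocol 13.1.2 and the SAE rules give opposite instructions for serious non-fatal GCA events, so GCA-attributed stroke and ischemic vision loss may be captured inconsistently in the safety tables

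*Protocol*

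**What the plan says.** **Keeping GCA findings out of AE capture.** Protocol 13.1.2 says: "Signs, symptoms and abnormal findings associated with active GCA should not be captured as Adverse Events in this study". The same sentence sends these findings to the efficacy data, in its words "but rather as flare related efficacy endpoint findings". Seriousness is not mentioned. Questions about classification go to the CRO-designated Medical Expert.

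**Requiring all SAEs.** Protocol 13.1.1 counts as an AE any clinically significant worsening "of a pre-existing condition that is temporally associated with the use of the study drug". Protocol 13.1.6 lists the seriousness criteria. On death it says: "Includes all deaths, even those that appear to be completely unrelated to study drug". SAEs after consent, "whether or not the SAEs are related to the study drug or study procedures, must be reported". Protocol 13.6 repeats the duty: "All SAEs, whether or not considered causally related to study drug or to the study procedure(s), have to be reported".

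**Events under both rules.** The cranial items of the flare definition (Protocol Synopsis, 8.4.1 and 12.2.1) include "Transient ischemic attack (TIA) or stroke related to GCA in the opinion of the Investigator", and visual findings such as ischemic retinopathy and optic neuropathy.

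**Analysis.** SAP 6.8.1 builds its by-arm safety tables from TEAEs and their serious subset. In SAP Table 1 the primary event is "Flare occurrence on or prior to week 26", counted once per subject.

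**The concern.** Take a subject hospitalised with a stroke that the investigator attributes to GCA. Section 13.1.2 tells the site not to record an AE. Sections 13.1.6 and 13.6 tell the same site to report an SAE. Whether the event reaches the safety tables then depends on the attribution to GCA and on which section the site follows.

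This is the first study of the drug in GCA, and stroke and permanent vision loss are among the worst outcomes of the disease. If their capture varies between sites, the by-arm count of serious events is unreliable for the outcomes that matter most. The plan also expects flares in unequal proportions of the two arms, so any loss need not be balanced.

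**Working it through.** **Step 1. Do the two rules overlap?**

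| | Covers | Exception |
|---|---|---|
| 13.1.2 | Signs, symptoms and findings of active GCA: not AEs | None for serious findings |
| 13.1.1 | Worsening of existing disease: an AE | None for GCA |
| 13.1.6, 13.6 | Any occurrence meeting a seriousness criterion: report | None for GCA |

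GCA-related stroke and ischemic visual loss are named GCA findings. If they lead to hospitalisation or lasting disability they also meet 13.1.6. The overlap is real, and neither section says which prevails.

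**Step 2. Follow an event recorded only under 13.1.2 through the SAP.**

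- *Safety tables (6.8.1).* With no AE record, the event is in neither the TEAE nor the TESAE tables.
- *Time to flare (6.7.2, Table 1).* A flare also needs CRP of at least 1 mg/dL and/or ESR of at least 30 mm/h, so a stroke with neither is not a flare. Only the first flare in the treatment period counts, so a stroke after a headache-led flare adds nothing. Subjects who stop treatment early without a flare are censored at end of treatment. A sensitivity analysis follows them to Week 26.
- *Time to signs/symptoms or imaging change (6.7.3.4).* This does not need a raised marker, but it uses the earliest date only and does not separate stroke from headache.
- *Taper completion without signs/symptoms (6.7.3.8).* This uses all assessments from taper completion to Week 26, again without identifying the type of event.
- *Washout.* GCA assessments continue at Weeks 30, 34 and 38, but no washout flare analysis is visible. Some endpoints are redacted, so one may exist.

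A related gap remains even when the AE is recorded. Subjects who flare must stop study drug, and the SAP ends the TEAE window 90 days after the last dose. As an illustration, a last dose at Week 4 closes the window at 4 + 90/7 = 16.9 weeks, while follow-up runs to Week 38.

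**Step 3. Deaths.** Every death is an SAE (13.1.6). All-cause deaths are listed (SAP 6.8.1), and death is a by-arm disposition reason (SAP 6.2). Only the underlying fatal GCA event could be missing, from the table of TEAEs resulting in death.

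**Step 4. Size.** Inputs from Protocol 8.6 and 14.2: 28 placebo and 42 KPL-301 subjects, with 50% and 85% flare-free at Week 26.

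- Check of the plan's figures: HR = ln(0.85)/ln(0.50) = 0.2345 (stated 0.234). Power at 20 events with 3:2 allocation is 87.3% by Freedman's formula and 88.8% by Schoenfeld's (stated 87%).
- Expected first flares: 28 × 0.50 = 14.0 on placebo and 42 × 0.15 = 6.3 on KPL-301, total 20.3 (stated about 20).
- The documents give no serious share. Assumed range:

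| Assumed serious share | Placebo | KPL-301 | Total |
|---|---|---|---|
| 5% | 0.7 | 0.3 | 1.0 |
| 10% | 1.4 | 0.6 | 2.0 |
| 20% | 2.8 | 1.3 | 4.1 |

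For this pool of flares the totals are upper bounds at each assumed share, because they suppose that every site follows 13.1.2 over 13.6. Serious GCA events without a preceding or accompanying flare by Week 26 lie outside the pool.

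**The case against.** The strongest reply is that the sections can be read together: 13.1.2 governs routine AE recording, while the SAE duty in 13.1.6 and 13.6 is mandatory and stands on its own. The Medical Expert is consulted on every suspected flare anyway and can settle classification. On that reading nothing is lost.

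This stands in part. It shows that loss is a risk of ambiguous wording, not an exclusion the plan prescribes. But the text does not state that reading, and referral to an expert sets no rule that all sites apply alike.

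Three stronger conclusions may tempt a reader, and the documents do not support them:

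- *GCA deaths drop out of the safety comparison.* They do not, as Step 3 shows.
- *The stopping criteria are blinded to these events.* In Protocol 17.1 the death, general grade 4 and hepatic triggers require relatedness to the product, which a stroke attributed to GCA would not normally meet even if filed as an SAE. Only the discretionary item on unforeseen events, or a cumulative review already triggered, might be affected.
- *The arms cannot be compared on these outcomes.* GCA assessments run to Week 38, flare work-up elements go into the eCRF, and Protocol 14.1 puts all clinical data in listings. What is missing is a consistent SAE rule and a by-arm table, not necessarily the data.

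**Conclusion.** The contradiction holds for serious non-fatal GCA events: stroke or TIA and ischemic visual events. They may be captured inconsistently and be missing from the by-arm TEAE and TESAE tables, and the visible efficacy endpoints do not reliably make up for it.

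The contradiction rests on the text alone and needs no numerical assumption. The size does: about 1 to 4 events at most among roughly 20 expected first flares, resting on a 5% to 20% serious share that the documents do not supply. In a trial of 70 subjects a difference of that order could matter in an SAE table. The point is worth correcting. It does not affect the validity of the primary efficacy analysis.

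**What to change.** **Protocol.** Reconcile 13.1.2 with 13.1.1, 13.1.6 and 13.6. State that the AE exemption covers only non-serious GCA findings, and that any GCA finding meeting a seriousness criterion is also recorded and reported as an SAE.

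**SAP 6.8.1.** Add one by-arm table of GCA-related ischemic events (vision loss, TIA, stroke) from first dose through Week 38, including events after a first flare and in washout. Build it from the GCA assessments and AE data already collected. The symptom categories that SAP 6.7.2 takes from the eCRF already include vision loss and TIA or stroke.

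**Cost.** One clarifying sentence and one table. Some events will appear in both efficacy and safety tables, which a footnote can explain. SAP 7.1 speaks of first doses in the past tense, so subjects had already been treated. GCA events recorded for them need a check against the seriousness criteria, or capture will differ before and after the change. Keeping non-serious flare symptoms out of the AE tables is reasonable and stays as it is.
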